3.2.3 Exploratory Objective Estimands

The estimands corresponding to the exploratory objectives are shown in Table 3.

Objective 1	Mean reduction from baseline in the number of migraine days per month by intensity (total; moderate or severe) in each month and over the entire course of the DBT Phase
Efficacy Endpoint	Changes from the OP in the number of migraine days per month in each month and over the entire DBT Phase by pain intensity (total; moderate or severe)
Summary	Changes from the OP by treatment group using descriptive statistics and linear mixed effects model with repeated measures, and difference between treatment groups from the model for the DBT migraine analysis set
Intercurrent Events	Study drug discontinuation: hypothetical strategy
	Non-study prophylactic migraine medication use: treatment policy strategy
	Nonstudy acute migraine-specific medication use: composite strategy
	Use of nonstudy other medication to treat headache (migraine or nonmigraine) or aura: treatment policy strategy
Objective 2	Proportions of subjects with \geq 50% reduction, \geq 75% reduction, and 100% reduction from baseline in the number of migraine days per month by pain intensity (total; moderate or severe) in each month and over the entire course of the DBT Phase
Efficacy Endpoint	Proportions of subjects with $\ge 50\%$ reduction, $\ge 75\%$ reduction, and 100% reduction from the OP in the number of migraine days per month in each month and over the entire DBT Phase by pain intensity (total; moderate or severe)
Summary	Percentages by treatment group, and difference in percentages between treatment groups using Mantel-Haenszel risk estimation for the DBT migraine analysis set
Intercurrent Events	Study drug discontinuation: composite strategy
	Non-study prophylactic migraine medication use: treatment policy strategy
	Nonstudy acute migraine-specific medication use: composite strategy
	Use of nonstudy other medication to treat headache (migraine or nonmigraine) or aura: treatment policy strategy
Objective 3	Mean reduction from baseline in the number of migraine days per week by pain intensity (total; moderate or severe) in each week of the first 4 weeks of the DBT Phase
Efficacy Endpoint	Changes from the OP in the number of migraine days per week during DBT in each week of the first 4 weeks by pain intensity (total; moderate or severe)
Summary	Changes from the OP by treatment group using descriptive statistics and linear mixed effects model with repeated measures, and difference between treatment groups from the model for the DBT first month migraine analysis set
Intercurrent Events	Study drug discontinuation: hypothetical strategy
	Non-study prophylactic migraine medication use: treatment policy strategy
	Nonstudy acute migraine-specific medication use: composite strategy
	Use of nonstudy other medication to treat headache (migraine or nonmigraine) or aura: treatment policy strategy

Table 3 Exploratory Objective Estimands

Objective 4	Mean reduction from baseline in the number of migraine days per month by intensity (total; moderate or severe) in each month and over the entire course of the OLE Phase
Efficacy Endpoint	Mean changes from the OP in the number of migraine days per month in each month and over the entire OLE Phase by pain intensity (total; moderate or severe)
Summary	Changes from the OP by treatment group using descriptive statistics for the OL rimegepant migraine analysis set
Intercurrent Events	Study drug discontinuation: while-on-treatment strategy
	Non-study prophylactic migraine medication use: treatment policy strategy
	Nonstudy acute migraine-specific medication use: composite strategy
	Use of nonstudy other medication to treat headache (migraine or nonmigraine) or aura: treatment policy strategy
Objective 5	Proportions of subjects with ≥ 50% reduction, ≥ 75% reduction, and 100% reduction from baseline in the number of migraine days per month by pain intensity (total; moderate or severe) in each month and over the entire course of the OLE Phase
Efficacy Endpoint	Proportions of subjects with $\geq 50\%$ reduction, $\geq 75\%$ reduction, and 100% reduction from the OP in the number of migraine days per month in each month and over the entire OLE Phase by pain intensity (total; moderate or severe)
Summary	Percentages by treatment group for the OL rimegepant migraine analysis set
Intercurrent Events	Study drug discontinuation: while-on-treatment strategy
	Non-study prophylactic migraine medication use: treatment policy strategy
	Nonstudy acute migraine-specific medication use: composite strategy
	Use of nonstudy other medication to treat headache (migraine or nonmigraine) or aura: treatment policy strategy
Objective 6	Mean number of acute migraine-specific medication days per month and acute migraine medication days per month in each month and over the entire course of the DBT Phase
Efficacy Endpoint	Mean number of acute migraine-specific medication days per month and acute migraine medication days per month in each month and over the entire DBT Phase
Summary	Values by treatment group using descriptive statistics and linear mixed effects model with repeated measures, and difference between treatment groups from the model for the DBT migraine analysis set
Intercurrent Events	Study drug discontinuation: hypothetical strategy
	Non-study prophylactic migraine medication use: treatment policy strategy
	Nonstudy acute migraine-specific medication use: not applicable
	Use of nonstudy other medication to treat headache (migraine or nonmigraine) or aura: treatment policy strategy for acute migraine-specific medication day and not applicable for acute migraine medication day
Objective 7	Mean number of acute migraine-specific medication days per month and acute migraine medication days per month in each month and over the entire course of the OLE Phase

Efficacy Endpoint	Mean number of acute migraine-specific medication days per month and acute migraine medication days per month in each month and over the entire OLE Phase
Summary	Values by treatment group using descriptive statistics for the OL rimegepant migraine analysis set
Intercurrent Events	Study drug discontinuation: while-on-treatment strategy
	Non-study prophylactic migraine medication use: treatment policy strategy
	Nonstudy acute migraine-specific medication use: not applicable
	Use of nonstudy other medication to treat headache (migraine or nonmigraine) or aura: treatment policy strategy for acute migraine-specific medication day and not applicable for acute migraine medication day
Objective 8	Mean change from baseline in MSQoL domain scores (restrictive role function, preventive role function, emotional function), MIDAS scores (total, absenteeism, presenteeism), EQ-5D-5L VAS score during the DBT and OLE Phases
Outcomes Research Endpoint	Mean change from baseline in MSQoL domain scores (restrictive role function, preventive role function, emotional function), MIDAS scores (total, absenteeism, presenteeism), EQ-5D-5L VAS score at Week 12 of the DBT Phase and Week 24 and Week 52 of the OLE Phase
Summary	• DBT Phase: Change from baseline by treatment group using descriptive statistics and linear regression model, and difference between treatment groups from the model for the DBT efficacy analysis set
	• OLE Phase: Change from baseline by treatment group using descriptive statistics for the OL rimegepant efficacy analysis set
Intercurrent Events	Study drug discontinuation: treatment policy strategy
	Non-study prophylactic migraine medication use: treatment policy strategy
	Nonstudy acute migraine-specific medication use: treatment policy strategy
	Use of nonstudy other medication to treat headache (migraine or nonmigraine) or aura: treatment policy strategy

4 ANALYSIS SETS, TREATMENT GROUPS, AND SUBGROUPS

4.1 Analysis Sets

The following analysis sets are used for statistical analyses, as applicable:

- Enrolled: subjects who signed informed consent and were assigned a subject identification number by the interactive web response system (IWRS), i.e., nonmissing informed consent date. This analysis set is used mainly to assess study population and in by-subject listings.
- Full: subjects in the enrolled analysis set who were assigned a randomized treatment group by IWRS, i.e., nonmissing IWRS randomization date. This analysis set is used mainly to assess study population.
- Safety: subjects in the enrolled analysis set who take ≥ 1 dose of study drug (DB or OL), i.e., nonmissing study drug start date. This analysis set is used to assess study population, exposure, and on-treatment safety, and produce select by-subject listings.
 - \circ DBT safety: subjects in the safety analysis set who take \geq 1 dose of DB study drug

(rimegepant or placebo), i.e., nonmissing DB study drug start date. This analysis set is used to assess study population, exposure, and on-DBT safety.

- \circ OL rimegepant safety: subjects in the safety analysis set who take ≥ 1 dose of OL rimegepant, i.e., nonmissing OL rimegepant start date. This analysis set is used to assess study population, exposure, and on-OL rimegepant safety.
 - Interim safety: subjects in the OL rimegepant safety analysis set with OL rimegepant start date – DB study drug last date > 7 days. This analysis set is used to assess post-DBT pre-OL rimegepant safety.
- DB or OL rimegepant safety: subjects in the safety analysis set who take ≥ 1 dose of DB or OL rimegepant, i.e., nonmissing DB or OL rimegepant start date. This analysis set is used to assess study population, exposure, and on-DB or OL rimegepant safety.
- Follow-up safety: subjects in the safety analysis set whose last contact date is in the followup safety analysis period. This analysis set is used to assess follow-up safety.
- DBT efficacy: subjects in the full analysis set who (1) are randomized only once, and (2) take
 ≥ 1 dose of DB study drug. This analysis set is used mainly to assess outcomes research
 endpoints during the DBT Phase.
 - DBT migraine: subjects in the DBT efficacy analysis set with ≥ 14 days of eDiary data (not necessarily consecutive) in both the OP and ≥ 1 month (4-week interval) during the DBT Phase (see Section 6.3.1.1). This analysis set is used to assess migraine days, headache days, acute migraine-specific medication days, and acute migraine medication days during the DBT Phase.
 - DBT first month migraine: subjects in the DBT efficacy analysis set with ≥ 24 days of eDiary efficacy data (not necessarily consecutive) in both the OP and in first month (4week interval) of the DBT Phase (see Section 6.3.3.1). This analysis set is used to assess migraine and headache days per week during the DBT Phase.
- OL rimegepant efficacy: subjects in the DBT efficacy analysis set who take ≥ 1 dose of OL rimegepant. This analysis set is used to assess outcomes research endpoints during the OLE Phase.
 - OL rimegepant migraine: subjects in both the DBT migraine and OL rimegepant efficacy analysis sets with ≥ 14 days of eDiary efficacy data (not necessarily consecutive) in ≥ 1 month (4-week interval) in the OLE Phase. This analysis set is used to assess migraine days, headache days, acute migraine-specific medication days, and acute migraine medication days during the OLE Phase.

See Section 7.1 for derived dates and Section 7.2 for analysis periods.

4.2 Treatment Groups

Treatment groups in the DBT Phase are rimegepant 75 mg ODT and placebo ODT. The safety analysis sets are assessed by as-treated treatment group (i.e., actual treatment received), the full, DBT efficacy, and migraine analysis sets are assessed by as-randomized treatment group, and the enrolled analysis set is assessed overall.

If a subject takes ≥ 1 dose of planned randomized DB study drug, then that subject is considered to have as-treated treatment group equal to as-randomized treatment group (see Section 6.2.6.2).

If there are non-randomized subjects who take study drug, then the as-randomized treatment group of "not randomized" is included for the full analysis set augmented with the safety analysis set.

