 - Tablets per month are assessed by the number of 4-week (28-day) intervals in which a subject exceeded select tablet counts from the DB study drug start date to the DB study drug end date, where the number of 4-week intervals are consecutive (see Section 6.3.1.1 for months). For example, suppose a subject takes 20 tablets through 4 weeks, 10 tablets after 4 weeks to 8 weeks, and 25 tablets after 8 weeks to 12 weeks. Thus, this subject is not considered to have taken ≥ 14 tablets (more than EOD frequency) per month for 3 consecutive months.
- > 1 DB tablet taken on any 1 day
- ≥ 1 non-scheduled DB study drug dosing day (see Section 9.4)
- Incorrect DB study drug taken
 - All the time. Defined as as-treated treatment group not equal to as-randomized treatment group, i.e., any of the following:
 - Subjects randomized to rimegepant who took (1) ≥ 1 tablet from a DB placebo wallet, and (2) no tablets from a DB rimegepant wallet
 - Subjects randomized to placebo who took (1) ≥ 1 tablet from a DB rimegepant wallet, and (2) no tablets from a DB placebo wallet.
 - At least once. Defined as any of the following:
 - Subjects randomized to rimegpant who took ≥ 1 tablet from a DB placebo wallet
 - Subjects randomized to placebo who took ≥ 1 tablet from a DB rimegepant wallet.
- Time on study drug > 14 weeks.

Results for all categories are displayed, even those with 0 counts.

OL Rimegepant Treatment Compliance

The by-subject listing of OL rimegepant treatment compliance is provided for the safety analysis set, and displays results for OL rimegepant treatment compliance parameters in separate columns: average DB exposure (tablets per month; see Section 6.2.6.1); percentage for OL rimegepant tablet count compliance; flags for the other parameters ("Y" or missing).

The frequency table of OL rimegepant treatment compliance is provided by treatment group for the safety analysis set, and displays the following categories:

- OL rimegepant tablet count compliance ≥ 80% from OL rimegepant start to later of last scheduled OLE Phase visit or OL rimegepant end. Tablet count compliance is derived as 100 × cumulative OL rimegepant exposure/required cumulative OL rimegepant exposure, where
 - Cumulative OL rimegepant exposure is defined in Section 6.2.6.1.
 - Required cumulative OL rimegepant exposure is derived as follows:

- Let n = OL maxdate OL rimegepant start date + 1.

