6.4.6 Safety Narrative Subject Identifiers

The by-subject listing of safety narrative subject identifiers is provided for the following select events as columns:

- Death in any analysis period for the enrolled analysis set
- SAE on DB or OL rimegepant or during follow-up for the DB or OL rimegepant safety analysis set
- AE leading to study drug discontinuation in any analysis period for the DB or OL rimegepant safety analysis set

- Event of special interest on DB or OL rimegepant for the DB or OL rimegepant safety analysis set:
 - \circ ALT or AST > 3x ULN
 - ALT or AST \ge 3x ULN and \ge 2x baseline
 - ALT or AST > 3x ULN concurrent with TBL > 2x ULN
 - \circ TBL > 2x ULN
 - Select hepatic-related AE, i.e., PT containing cirrhosis, hepatic failure, hepatitis, jaundice, or liver failure
 - Suicidality AE.

Refer to the Core SAP for additional details.

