 - Before the final database lock: OL rimegepant end date derived only for subjects with "yes" or "no" response to the phase completion question on the OLE Subject Status or Follow-up Subject Status CRF
 - Final database lock: OL rimegepant end date

This is an analysis period reference date.

- DB or OL rimegepant start date: study drug start date for subjects whose as-treated DB treatment group is rimegepant; OL rimegepant start date for subjects whose as-treated DB treatment group is placebo. This is an analysis period reference date.
- DB or OL rimegepant end date: study drug end date for subjects whose as-treated DB treatment group is rimegepant; OL rimegepant end date for subjects whose as-treated DB treatment group is placebo
- DB or OL rimegepant last dose date: study drug last date for subjects whose as-treated DB treatment group is rimegepant; OL rimegepant last date for subjects whose as-treated DB treatment group is placebo. This is an analysis period reference date.
- OP start date: earliest of the following: screening visit date 1 day; eDiary efficacy date. This is an analysis period reference date.
- OP end date:
 - \circ If the study drug start date is nonmissing: study drug start date 1 day
 - If the study drug start date is missing and the randomization date is nonmissing: randomization date 1 day
 - \circ $\,$ If both study drug start date and randomization date are missing: last contact date

This is an analysis period reference date.

- Last contact date:
 - 1. Earliest complete death date from the AE CRF, if it exists.
 - 2. Otherwise, the latest complete date of the following: AE start or end; ECG; eDiary finding; informed consent; dose; IWRS randomization; laboratory test collection; non-study medication start or end; physical exam; physical measurement; procedure; rating scale; questionnaire; vital sign; visit.
 - 3. If the last contact date is after the most recent raw database creation date, then it is set to the most recent raw database creation date.
- Death date: refer to the Core SAP.

No imputations are performed on these derived dates unless otherwise specified.

Refer to the Core SAP for the definition of complete dates.

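### The SAP's DB or OL rimegepant safety set requires one rimegepant dose, but its start date is derived so that a placebo-randomised subject who took some double-blind rimegepant has no date or a late one

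*SAP*

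**What the plan says.** The SAP supplied is for the prevention study C4951021. Four of its sections bear on this point.

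- **Section 4.2 (treatment groups).** "The safety analysis sets are assessed by as-treated treatment group (i.e., actual treatment received". The next paragraph sets a convention for mixed dosing: "If a subject takes ≥ 1 dose of planned randomized DB study drug, then that subject is considered to have as-treated treatment group equal" to the randomised group. One planned tablet is therefore enough.
- **Section 4.1 (analysis sets).** The DB or OL rimegepant safety set is "subjects in the safety analysis set who take ≥ 1 dose of DB or OL rimegepant, i.e., nonmissing DB or OL rimegepant start date".
- **Section 7.1 (derived dates).** The DB or OL rimegepant start date is "study drug start date for subjects whose as-treated DB treatment group is rimegepant" and "OL rimegepant start date for subjects whose as-treated DB treatment group is placebo". The end date and last dose date follow the same split.
- **Section 6.2.6.2 (compliance).** The mixed case is foreseen. The table of incorrect double-blind drug has an at-least-once row that includes "Subjects randomized to placebo who took ≥ 1 tablet from a DB rimegepant wallet". A separate row covers subjects who took the wrong drug throughout: "All the time. Defined as as-treated treatment group not equal to as-randomized treatment group". Only that second situation changes the as-treated group.

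Section 6.4.6 selects narratives on the same set, for example "SAE on DB or OL rimegepant or during follow-up for the DB or OL rimegepant safety analysis set". Section 6.2.6.1 counts cumulative DB or OL rimegepant tablets by wallet number, but measures time on drug from the Section 7.1 dates.

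**The concern.** Section 4.1 treats taking a rimegepant dose and having a start date as the same thing. Section 7.1 makes them differ for a placebo-randomised subject who received some double-blind rimegepant. A programmer who follows the first half of the definition includes that subject; one who follows the second half may not.

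The set feeds the combined AE tables and exposure-adjusted AEs (Section 6.4.1.5), the combined LFT elevation tables and time to first LFT elevation (Section 6.4.2.2), and most narrative selection (Section 6.4.6). Secondary objectives 8 to 10 concern subjects treated with rimegepant, and these subjects were treated with it. A serious event or liver elevation on that exposure could be absent from the combined rimegepant outputs and get no narrative.

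**Working it through.** No figure in the plan bears on this, so the check applies the rules of Sections 4.2, 7.1 and 4.1 to hypothetical placebo-randomised subjects. Every-other-day dosing over 84 days gives 84/2 = 42 tablets, on days 1, 3, ..., 83. In the mixed history, the 14 doses on days 1 to 27 are placebo and the 28 doses on days 29 to 83 are rimegepant. Open-label drug, if taken, starts on day 86.

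| Double-blind tablets taken | OL drug | As-treated group | Start date | In the set | DB rimegepant doses on or after start date |
|---|---|---|---|---|---|
| 14 placebo, 28 rimegepant | none | placebo | missing | no | 0 of 28 |
| 1 placebo, 41 rimegepant | none | placebo | missing | no | 0 of 41 |
| 14 placebo, 28 rimegepant | day 86 | placebo | day 86 | yes | 0 of 28 |
| 42 rimegepant | none | rimegepant | day 1 | yes | 42 of 42 |

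The fourth row shows that wrong drug throughout is handled correctly. The second row is the limit of the rule, not a likely case, because each wallet holds 8 tablets of one type.

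**Exposure mismatch in the third row.** Suppose, for illustration, 42 open-label tablets every other day, the last on day 86 + 2 × 41 = 168.

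- Tablets by wallet: 28 + 42 = 70.
- Time on drug under Section 7.1: (168 − 86 + 1)/7 = 83/7 = 11.86 weeks.
- Average under Section 6.2.6.1: 4 × 70/11.86 = 23.6 tablets per month.
- With the start date at the first rimegepant tablet (day 29): (168 − 29 + 1)/7 = 20 weeks, and 4 × 70/20 = 14.0 tablets per month, which is the every-other-day rate.

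The double-blind rimegepant tablets enter the numerator, but their time does not enter the denominator.

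**Narratives.**

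- Without open-label drug, the subject is outside the set, so serious, special-interest and discontinuation events are not selected.
- With open-label drug, discontinuation events are selected in any analysis period and serious events during follow-up are selected. Serious and special-interest events on the double-blind rimegepant exposure precede the start date and so are not on DB or OL rimegepant.
- Deaths are selected from the enrolled set in both cases.

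**Number affected.** The documents give no mis-dosing rate. Assuming 0.5% to 2% of about 245 placebo subjects: 245 × 0.005 = 1.2 and 245 × 0.02 = 4.9. Section 2.1 expects about 400 of 490 randomised subjects to enter the extension, so 1 − 400/490 = 18% would not. If mis-dosed subjects enter at that rate, 0.2 to 0.9 subjects have no date and the rest have a late one.

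**The case against.** The strongest reply is that this is rare, visible and covered by a prespecified convention.

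- **Most affected subjects stay in the set.** A reader might infer that every mixed-dose placebo subject drops out of it. That is not so: those who take open-label drug remain, with a late date. The average entry rate may understate exclusion among subjects with events, because Section 2.1 makes entry depend on completing double-blind treatment, continued eligibility and laboratory review.
- **The cases can be traced.** The study-drug listing gives dosing date and wallet type. Incorrect drug appears in the compliance table and as a relevant protocol deviation. The AE and LFT listings cover the enrolled set. This stands, but listings label the subject by randomised group, so a reader must cross-match, and the set, dates and narrative selection remain uncorrected.
- **The convention is symmetric.** A reader might infer that the rule flatters rimegepant. The documents do not support that. A rimegepant-randomised subject given some placebo stays in the rimegepant group, with a start date that may precede the first rimegepant tablet, so events on placebo count under rimegepant. Nothing suggests that one mix-up is commoner than the other.
- **The as-treated rule is explicit.** Moving every subject with one rimegepant tablet to the rimegepant column would be just as arbitrary: 1 rimegepant and 41 placebo tablets would then count as rimegepant. This stands, and no change to Section 4.2 is proposed.
- **Part of the machinery is elsewhere.** The Core SAP holds most safety-period definitions and was not supplied. However, the set definition and derived dates are explicit here, Section 7.1 names the start date as an analysis period reference date, and Section 6.4.1.5 uses it as such.

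**Conclusion.** As written, the definition in Section 4.1 contradicts itself for a case that the SAP foresees. A placebo-randomised subject who took at least one placebo tablet and at least one double-blind rimegepant tablet is either outside the DB or OL rimegepant safety set despite having taken rimegepant, or inside it with a start date after that exposure. The severity is minor: probably a handful of subjects at most, on an assumed rate, and fewer with a reportable event.

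The conclusion assumes that the Core SAP does not override the Section 7.1 dates. It concerns the SAP text only. The protocol supplied is for C4951022, a single-attack acute study without these wallets or an extension, so the point could not be checked against the SAP's own protocol.

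**What to change.** Leave the as-treated convention in Section 4.2 unchanged. In Section 7.1, for all subjects, derive the DB or OL rimegepant start and end dates from the earliest and latest dose with a valid DB rimegepant or OL rimegepant wallet number. Derive the last dose date in the same way, keeping its existing conditions before final database lock. The dates then match the dose wording of Section 4.1 and the tablet count in Section 6.2.6.1. Select the Section 6.4.6 narratives on the set so defined.

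No new data are needed, because Section 6.2.6.1 already merges wallet type by wallet number. The work is a text change and a small change to three derivations.

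The cost is that, for a mixed-dose subject, placebo time between rimegepant doses counts as time on rimegepant, as do events in that interval. For example, one wrong 8-tablet wallet on days 1 to 15, then placebo, then open-label drug from day 86 adds days 16 to 85: 70/365.25 = 0.19 patient-years. For 4.9 subjects that is 4.9 × 0.19 = 0.9 patient-years. Full double-blind exposure in the rimegepant arm alone is about 245 × 84/365.25 = 56 patient-years, so the inflation is under 2% even before open-label time is added.

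Footnote these subjects in the affected tables. The footnote should also cover a mixed-dose subject without open-label drug, who would now appear in the column that Table 4 labels as double-blind placebo followed by open-label rimegepant.
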